8.2.5 Prognostic factor analyses

Data of this trial will be added to the EORTC Recurrent GBM data warehouse for further pooled analyses of prognostic factors and other research objectives.

8.2.6 Data re-coding and display

Frequency tables will be tabulated (by treatment group or otherwise) for all categorical variables by the levels of the variables as they appear on the CRF (with %). Categories with a text field specification will be tabulated as categories and then supplemented by a listing with the following information for the patients fulfilling the condition for the specification (patient id, institution, treatment group, value of the item and text field contents).

Dates relating to events prior to entry will be presented as the delay in days (or weeks, months, or years) between the past event and the date of entry (date of randomization – date of past event + 1) and presented using the median and range. For example, on the randomization checklist, the date of last administration of prior treatment (or the date of first diagnosis of the cancer) will be presented as the time elapsed (in days, weeks, months or years, as appropriate) since the day of the last administration and the date of entry on study (date of randomization – last administration/diagnosis +1).

Other delays (eg. re-treatment delays) are presented as continuous variables using the median and range.

Continuous variables for which a coding system exists (such as for laboratory data) will be recoded into categories (for adverse events, the grading scale specified in the protocol will be used). Whenever no specific scale exists, lab data will be categorized based on the normal range: for example, below the lower normal limit (when appropriate), within the normal range, above the upper normal limit (ULN) and the degree to which it is above the ULN (for example > 2.5 x ULN, > 5 x ULN, > 10 x ULN). For laboratory data, the nadir is generally displayed. The nadir in a given cycle is the lowest laboratory value in that cycle; the overall nadir for a patient is the lowest laboratory value among all cycles.

Other continuous variables (for example age, dose ...) are presented using the median and range (minimum, maximum).

If appropriate, continuous data may also be presented in categories (for example, age may also be grouped in decades).

8.3 Interim futility analyses

At interim analysis one or both of the ABT-414 arms might be discontinued based on lack of efficacy for PFS (Reject H1 in favor of H0) according to RANO criteria assessed by IRC.

It is assumed that median PFS is 2.6 months in the control arm and 4.8 months in the treatment arms corresponding to HR equal to 0.54. Assuming an accrual rate of 10 patients/month and activation phase of one year, at least 45 PFS events should be observed. Analyses will be performed when at least 31 PFS events are observed in each comparison. Treatment arms which did not show a minimum level of efficacy, defined as a computed treatment PFS HR lower than 0.91 will be discontinued. The trial will continue with remaining treatment arm(s) and control. There will be no interruption of accrual for the interim analysis.

Treatment PFS HR will be presented with two-sided 95% CI. However, since efficacy data will be analyzed for futility purpose, an alpha spending of 0.00001 will be allocated to the futility analysis. For the final analyses, efficacy endpoint will be tested at a nominal 1-sided alpha level of 0.02499.

For each of the two treatment arms the probability of stopping for futility at the interim is 7.4% if the true PFS HR is 0.54 and 60% if the true PFS HR is 1.0 (no benefit).

Based on the assumed accrual rates and treatment effects stated above, the interim futility analysis is expected to be performed when 90 randomized patients (30 patients per arm) have completed approximately 4 months of follow-up.

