5.4 Withdrawal criteria

Whatever the disease status, study treatment will be discontinued in case of:

- ◆ disease progression
- ◆ patient refusal
- ◆ intolerable toxicity precluding further protocol therapy
- ◆ patient's best interest
- ◆ start of any other anti-cancer agent/modality (surgery at recurrence is allowed)
- ◆ pregnancy

Patients discontinuing therapy in the absence of progression should not receive other cancer treatment before their disease progresses, unless this is clearly not in the interest of the patient. If, after treatment discontinuation, there is additional clinical information leading the investigator to conclude that the reason for discontinuation is no longer valid (except for toxicity), the subject may resume study treatment as long as no other chemotherapy, radiotherapy, immunotherapy, NovoTTF, or other treatment with antineoplastic intent has been received, with the exception of surgical intervention that yields histology not demonstrative of tumor progression. In case of toxicity in the combination arm that is

clearly attributable to either TMZ or ABT-414, that drug can be discontinued and the other can be continued. Patients that discontinue study treatment for toxicity, patient refusal and other reasons remain 'on study' and must be followed according to the follow-up schedule for progression, survival etc unless patient specifically withdraws consent from all further data collection for the study (this decision should be clearly documented e.g in the medical notes).

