6.4 After end of treatment

Every 12 weeks (+/- 14 days) since last protocol treatment administration until death or loss to follow up:

- Survival follow up
- Further anti-cancer treatments/modalities
- Physical examination including WHO performance status and neurological examination
- Ocular examination if clinically indicated
- Vital signs if clinically relevant
- Steroid intake
- Concomitant medication collection if clinically relevant
- Assessment of all adverse events according to CTCAE 4.0 (i.e. for events not resolved after the end of treatment and new events related to study treatment)

If a subject is unable to return to the clinic for this visit, survival follow up and other assessments as appropriate may be completed via phone.

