8.2.2 Analysis populations

- ◆ Intention-to-treat population (ITT): All randomized patients will be analyzed in the arm they were allocated by randomization.
- ◆ Per protocol population (PP): All patients who are eligible and have received at least one dose of the study drug (i.e. one dose of lomustine or TMZ (arm 3), of ABT-414 (arm 2) and of TMZ and ABT-414 (arm 1)). Patients will be classified and analyzed in the arm they were assigned at the time of randomization.
- ◆ Safety population (SP): All randomized patients who have received at least one dose of the study drug (i.e. one dose of lomustine or TMZ (arm 3), of ABT-414 (arm 2) and of TMZ and ABT-414 (arm 1)). Patients will be classified according to treatment received.

A patient will be considered to be eligible if he/she did not have any deviation from the patient entry criteria listed in chapter 3 of the protocol. Potential eligibility problems will be assessed by the Clinical Research Physician at time of medical review.

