8.2.3 Statistical methods

8.2.3.1 Overall Survival

In the ITT:

OS will be compared between arm 1 versus arm 3 and/or arm 2 versus arm 3 when 170 deaths (118 per comparison) are observed.

Differences between the treatment groups in OS will be assessed by a Logrank test stratified by the randomization stratification factors, testing the null hypotheses (H1: Arm 1 is not superior to Arm 3 in OS; H2: Arm 2 is not superior to Arm 3 in OS, respectively). The hazard ratios of the two treatment arms over the control arm will be calculated by Cox's proportional hazards model (score test) stratified by randomization stratification factors.

The OS probability at 12 months (OS12), at 2 years (OS24) and the median OS (mOS) will be estimated from the Kaplan-Meier OS curve. Two-sided 95% CI will be computed based on the Greenwood's formula. For the median the Reflected Method will provide two-sided 95% CI.

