8.2.3.6 Global strategy to control type I error for efficacy endpoints

To meet global regulatory requirements, a multiple testing strategy for the following ordered endpoints will be implemented to control the family-wise type I error (alpha) for comparisons of Arm 1 (ABT-414 + TMZ) versus Arm 3 (TMZ/lomustine) and Arm 2 (ABT-414 alone) versus Arm 3 with respect to overall survival (OS) and the pre-defined secondary efficacy endpoints, namely progression-free survival (PFS), objective response rate (ORR), and OS for patients with EGFR vIII mutation.

The following null hypotheses are considered:

H1: Arm 1 is not superior to Arm 3 in OS.

H2: Arm 2 is not superior to Arm 3 in OS.

H1a: Arm 1 is not superior to Arm 3 in PFS.

H2a: Arm 2 is not superior to Arm 3 in PFS.

H1b: Arm 1 is not superior to Arm 3 in ORR.

H2b: Arm 2 is not superior to Arm 3 in ORR.

H1c: Arm 1 is not superior to Arm 3 in OS among EGFR vIII mutated patients.

H2c: Arm 2 is not superior to Arm 3 in OS among EGFR vIII mutated patients.

[figure not shown]
To maintain the overall type I error control for the study, the following null hypotheses will be tested in a fixed sequence of {H1, H2, H1a, H2a, H1b, H2b, H1c, H2c} in order at a 1-sided 2.5% level of significance. Hypothesis H1 will be tested first at a 1-sided 2.5% level. No further tests will be performed if H1 is not

rejected. Each hypothesis will be tested in order specified above if H1 and all preceding hypotheses show statistically significant results at the 1-sided 2.5% level of significance. Otherwise testing in the fixed sequence will stop.

All other endpoints, e.g., PFS in EGFRvIII mutated, global health/QoL status (GHQs), and neurological disease-free survival (NDFS) are considered exploratory and will be tested at a 2-sided 5% level of significance.

Arm 1 vs. Arm 3

Arm 2 vs. Arm 3

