4.6 Type I Error Adjustment Procedures for Multiple Testing

Although Section 8.2.3.6 of the study protocol dated November 25, 2015, describes a different testing order, the multiple testing strategy was revised per diagram (Figure 2) in version 1.0 of the SAP finalized prior to the interim analysis of efficacy data. Given the clinical importance of an overall survival (OS) benefit in recurrent GBM subjects, comparing first OS of combination arm (ABT-414 + TMZ) vs. control and next OS of ABT-414 monotherapy vs. control, followed by comparison of other secondary efficacy endpoints in a similar sequence, is considered a simple and more clinically relevant approach to test the various study hypotheses. At the final analysis, the treatment effects will be tested at the adjusted significance level mentioned in the previous section. The proposed multiple testing strategy based on the above fixed hierarchical sequence preserves the family-wise type-I error at 1-sided 2.5% level. This change was made by consensus agreement among the study sponsors (EORTC and AbbVie Inc.) without any knowledge of unblinded efficacy data from the trial and prior to interim futility analysis.

To describe the multiplicity adjustment procedure fully, consider the following null hypotheses:

H1: Arm 1 is not superior to Arm 3 in OS.

H2: Arm 2 is not superior to Arm 3 in OS.

H1a: Arm 1 is not superior to Arm 3 in PFS.

H2a: Arm 2 is not superior to Arm 3 in PFS.

H1b: Arm 1 is not superior to Arm 3 in ORR.

[figure not shown]
H2b: Arm 2 is not superior to Arm 3 in ORR.

H1c: Arm 1 is not superior to Arm 3 in OS among EGFR vIII mutated subjects.

H2c: Arm 2 is not superior to Arm 3 in OS among EGFR vIII mutated subjects.

To maintain the overall type I error control for the study, these null hypotheses will be tested in a fixed sequence of {H1, H2, H1a, H2a, H1b, H2b, H1c, H2c}. Hypothesis H1 will be tested first, and no further tests will be performed if H1 is not rejected. Thereafter, each hypothesis will be tested in the order specified if and only if H1 and all preceding null hypotheses are rejected. Otherwise testing in the hierarchical sequence will stop.

Figure 2. Testing Procedure

All other endpoints, e.g., PFS in EGFRvIII mutated, global health/QoL status (GHQs), and neurological disease-free survival (NDFS) are considered exploratory and will be tested at a 2-sided 5% level of significance.

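### If one ABT-414 arm is dropped at the futility look, does the plan leave the other arm's tests undefined?

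*Protocol*

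**What the plan says.** Protocol 8.3 and SAP 4.5 drop an ABT-414 arm whose observed PFS hazard ratio is not below 0.91, and "The trial will continue with remaining treatment arm(s) and control". SAP 4.5 adds that the decision rests on all the interim data and on IDMC advice.

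The testing order is H1 (Arm 1 OS), H2 (Arm 2 OS), then PFS, ORR and OS in EGFRvIII-mutated patients, with Arm 1 before Arm 2 each time. In the Protocol, after the first hypothesis that is not rejected, "Otherwise testing in the fixed sequence will stop" (8.2.3.6). In SAP 4.6, "each hypothesis will be tested in the order specified if and only if H1 and all preceding null hypotheses are rejected". SAP 4.6 explains the order as "considered a simple and more clinically relevant approach to test the various study hypotheses" and says that it was agreed before the interim, without knowledge of unblinded efficacy data.

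Three other provisions bear on a dropped arm:

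- ITT population: "All randomized patients will be analyzed in the arm they were allocated by randomization" (Protocol 8.2.2).
- Patients who stop treatment remain on study and "must be followed according to the follow-up schedule for progression, survival etc" (Protocol 5.4).
- Follow-up visits run every 12 weeks "since last protocol treatment administration until death or loss to follow up" (Protocol 6.4).

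On timing, Protocol 8.2.3.1 states that "OS will be compared between arm 1 versus arm 3 and/or arm 2 versus arm 3" at 170 deaths, 118 per comparison. For end of study, Protocol 8.5 gives 170 deaths for two comparisons or 118 for one. SAP 6.0 asks for 118 in each comparison with control and has no separate clause for one comparison.

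**The concern.** The futility rule can leave one experimental arm, but the testing sequence interleaves two. No sentence says whether a dropped arm's hypotheses are skipped, count as failures, or are tested on the patients already randomized. The answer matters most if Arm 1 goes, because H1 is the gate for everything. Arm 2 could then finish the trial with a good result and no confirmatory OS claim. If Arm 2 goes, Arm 1's PFS, ORR and subgroup tests wait behind H2.

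The end-of-study wording adds to the doubt. If the SAP's condition covers a dropped comparison too, the trial might have to wait for deaths in an arm that stopped recruiting early. SAP 4.5 records that the futility reports went to the IDMC on 21 September 2016, but not which arms continued.

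**Working it through.** **1. The plan's own figures reproduce.**

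- Deaths per comparison (Protocol 8.1.1: HR 0.54, one-sided 2.5%, power 91.7%), by Schoenfeld: 4 × (1.960 + 1.385)² / (ln 0.54)² = 4 × 11.19 / 0.3797 = 118.
- Futility stop (Protocol 8.3: 31 PFS events, boundary 0.91): SE of log HR = 2/√31 = 0.359. At HR 0.54, P(observed HR ≥ 0.91) = 1 − Φ[(ln 0.91 − ln 0.54)/0.359] = 1 − Φ(1.453) = 7.3% (plan: 7.4%). At HR 1.0 it is 60.4% (plan: 60%).
- Overall power with independent PFS and OS: 0.917 × (1 − 0.074) = 0.849 (plan: about 85%).

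**2. What the text does with a dropped arm.** The sequence has no exceptions, ITT is everyone randomized, and survival is followed to death. So if Arm 1 is dropped, H1 is still tested, on all patients randomized to Arm 1, and H2 follows only if H1 is rejected. Nothing has to be invented to run this.

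**3. Type I error.** A fixed sequence at full alpha is safe in this form. A simulation of interim PFS (31 events) and final OS (118 events), with between-arm correlation 0.5 from the shared control, gives these error rates over H1 and H2 when neither arm works. The PFS-OS correlation is an assumption.

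| PFS-OS correlation | 0 | 0.3 | 0.5 | 0.7 |
|---|---|---|---|---|
| Dropped hypothesis blocks later ones | 1.0% | 1.7% | 2.1% | 2.4% |
| Dropped hypothesis is skipped | 1.4% | 2.3% | 2.8% | 3.1% |

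Skipping, which would help a lone Arm 2, can exceed 2.5%.

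**4. How often the case arises.** With both HRs at 0.54 and the boundary applied mechanically, only Arm 1 is dropped in 5.2% of trials, and only Arm 2 in 5.2%. With Arm 1 at 0.75 and Arm 2 at 0.54, only Arm 1 is dropped in about 24%.

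**5. Size of Arm 1 if dropped.** The planned look (90 patients with 4 months of follow-up) falls at month 13, when 120 + 20 = 140 are randomized. Accrual was not interrupted, and the IDMC saw results on 21 September 2016 after a 1 July cut-off. That is 2.7 months at 20 per month, about 54 patients. (140 + 54)/3 is about 65 per arm.

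**6. Consequence with 65 Arm 1 patients.** Simulation assumptions: exponential OS (control median 7 months) and PFS (2.6 months), Arm 1's PFS HR equal to its OS HR, Arm 2 at 0.54, Arms 2 and 3 filled to 80 each, analysis at 118 deaths in Arms 2 and 3, PFS-OS correlation 0 or 0.5. Results are given that only Arm 1 was dropped.

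| Arm 1 HR | H1 and H2 both rejected (correlation 0 / 0.5) | Median wait for 118 deaths in Arms 1+3 after Arms 2+3 reach 118 |
|---|---|---|
| 0.54 | 82.8% / 72.3% | 2.9 to 3.5 months |
| 0.75 | 32.8% / 23.0% | 0.0 |
| 1.0 | 2.5% / 1.2% | −2.1 months |

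H2 tested without the gate has power 89.7% to 91.7%. The expected loss at equal effects runs from 0.052 × (0.897 − 0.828) = 0.4 points to 0.052 × (0.917 − 0.723) = 1.0 points.

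**7. Is the loss due to dropping or to the order?** At HR 0.75 with the full 118 deaths, H1's power is Φ(√118/2 × 0.2877 − 1.960) = Φ(−0.40) = 35%. H2 could therefore pass the gate in at most 35% of trials even with no arm dropped. The 23% to 33% in the table comes mostly from the chosen order.

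**8. Death counts.** Protocol 8.5 and SAP 6.0 both define end of study. Protocol 8.2.3.1 times the OS comparison, and its and/or wording already allows for one arm. If one comparison remains, SAP 6.0's 118 in each comparison is the same 118 as in Protocol 8.5. The wait in the table arises only if a discontinued arm must also reach 118.

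**The case for a change.** The best case for a change is that careful readers can differ. One would treat a dropped arm's hypothesis as failed, another would test it on the truncated ITT set, and a third might skip it. Step 3 shows that the third choice is not harmless, so an unwritten decision after the interim would be open to challenge. If Arm 1 is much worse than Arm 2, the branch is not rare (24% at Arm 1 HR 0.75), and a good Arm 2 would usually get no claim. Protocol 8.5 also ties its death count to maturity for the primary endpoint, so the SAP's missing clause is not pure housekeeping. A final SAP could reasonably say which arms are still under test.

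What stands is that the wording is silent and that SAP 6.0 is ambiguous if an arm was dropped. The rest does not carry. Skipping has no support in either document, and the other two readings both protect type I error. The lost claim for Arm 2 is the ordinary cost of a pre-specified order with stated reasons. Writing the default down would alter no test, level, population or event count.

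**Conclusion.** No change follows. This is a gap in wording that an analyst fills correctly by applying the plan as written: same order, same levels, a dropped arm tested on everyone randomized to it, and survival followed to death. Under the plan's equal-effect assumption the cost is about 0.4 to 1.0 percentage points of power for H2. A delayed end of study, at most about 3.5 months, needs an unnatural reading of SAP 6.0.

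These sizes rest on about 65 Arm 1 patients, a mechanical 0.91 rule and an assumed PFS-OS correlation of 0 to 0.5. They grow if Arm 1 is clearly worse than Arm 2, but most of that is the price of testing Arm 1 first.

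The case is also probably moot. SAP 3.0 cites protocol version 6 of January 2017, and Protocol Appendix L refers to version 7, so both documents postdate the September 2016 look. Both still describe three arms and all eight hypotheses, and SAP 4.5 still sets a final level for each comparison. That is an inference, since the outcome of the look is not stated, but the conclusion does not depend on it.

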8.4 Re-randomization Test

The robustness of the results to the use of the minimization randomization algorithm will be evaluated by performing a re-randomization test on the primary efficacy analysis, the stratified log-rank test and Cox's proportional hazards model (score test) stratified by randomization stratification factors, to compare the duration of overall survival between the treatment arm(s) and the control.

The re-randomization test will be performed as follows:

- The procedure will use 50,000 replications of the ITT population (all randomized patients).
- Based on the value of their randomization stratification factors, for each replicate, patients will be (virtually) re-assigned to treatments using the original minimization randomization algorithm in the order in which they were randomized into the trial.
- For each replicate the stratified log-rank test statistic and Cox's proportional hazards model (score test) stratified by randomization stratification factors comparing the duration of overall survival will be computed.
- The re-randomization test p-values will be the fraction of replications where the log-rank and Cox' model-based p-values from the replicates are less than or equal to the corresponding p-values from the original analysis.

Robustness of the results will be established if the re-randomization test p-values are then found to be comparable to the corresponding p-values from the original analysis.

8.5 End of study

End of study occurs when all of the following criteria have been satisfied:

1. The trial is mature for the analysis of the primary endpoint as defined in the protocol (i.e. at least when 170 deaths will be observed for two comparisons and 118 deaths for one comparison).
2. The database has been fully cleaned and frozen for this analysis.
3. Forty nine days after all patients have stopped protocol treatment.

9 Trial Governance and Data Monitoring

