8.1 Statistical design

8.1.1 Sample size

This is a comparative randomized open label multicenter/multiarm phase II trial. Overall Survival (OS) is the primary endpoint.

Based on literature review, a median OS of 7 months is expected in the mixed control arm (lomustine or TMZ). Based on a one-sided logrank test, at an overall significance level of 2.5% and a power of 91.7% (accounting for the global testing strategy), a total of 170 deaths (118 per comparison, i.e. monotherapy ABT-414 versus control and combination ABT-414 + TMZ versus control) are needed to detect an increase of median OS to 12.9 months in the treatment arms corresponding to a Hazard Ratio (HR) equal to 0.54 (i.e. a reduction in the hazard of death of 46%). Assuming a monthly accrual of 10 patients during month 1 to 12 and 20 patients per month after 12 months, 240 patients can be recruited within 18 months. A follow-up duration of 13 months after end of accrual is required to observe the 170 deaths.

There will be an interim futility analysis organized after observation of 45 PFS events (see section 8.3).

Provided that PFS and OS effects are independent, the overall power of the study is estimated to be approximately 85%. However, treatment effect on PFS and on OS may reasonably be assumed to be positively correlated, and hence the overall power of the study accounting for the interim analysis is expected to exceed 85%.

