A prior medication is defined as any medication with an end date prior to the date of randomization and collected on the electronic case report forms (eCRFs). A concomitant medication is defined as any drug that started on the day of or after randomization, but not 35 days after the last protocol drug administration. Medications with a start date prior to the date of randomization and continuing after randomization are also classified as concomitant medications. A medication will also be considered a concomitant medication if one of the following three cases occur: (1) the start date is missing and the end date is

either after or on the day of randomization; (2) the start date is not missing but not 35 days after the last protocol drug administration and the end date is missing; (3) both the start date and the end date are missing.

End of Study

End of study occurs when all of the following criteria have been satisfied:

- At least 118 deaths have been observed for each treatment arm comparison versus control,
- Thirty five days have passed since all subjects have stopped protocol treatment, and
- The database has been fully cleaned and frozen for analyses.

7.0 Demographics, Baseline Characteristics, Medical History, Previous/Concomitant Medications, and Prior Oncology Therapies

Data for demographic, baseline characteristics, medical history, previous/concomitant medications, and prior oncology therapies will be summarized for each treatment arm and overall on the ITT population.

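### With both ABT-414 arms open, Protocol 8.5 sets OS maturity at 170 pooled deaths and the SAP at 118 in each comparison; nothing says which governs

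*Protocol*

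**What the plan says.** The milestone for the primary OS analysis appears in several places.

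- **Protocol 8.1.1** (repeated in the summary) requires "a total of 170 deaths (118 per comparison") to detect the target effect, "at an overall significance level of 2.5% and a power of 91.7"%.
- **Protocol 8.2.3.1** compares OS "when 170 deaths (118 per comparison) are observed". Both counts are given, with no rule for the case in which they are not reached together.
- **Protocol 8.5** defines maturity as "at least when 170 deaths will be observed for two comparisons and 118 deaths for one comparison". With two comparisons open, the only number is the pooled one.
- **SAP 4.4** states the requirement as 118 deaths per comparison. The figure 170 does not appear in the SAP.
- **SAP 6.0, End of Study**, has as its event condition: "At least 118 deaths have been observed for each treatment arm comparison versus control".

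SAP 4.4 also states that the same target effect is assumed for both ABT-414 arms. Protocol 8.2.3.6 tests H1 (Arm 1 versus Arm 3, OS) first and stops all testing if it is not rejected.

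**The concern.** The stated power belongs to the number of deaths in the comparison being tested. A pooled count across three arms fixes that number only if the split of deaths between arms is known. Arm 2 deaths add nothing to H1, but they do count towards 170. If monotherapy is the weaker arm, its deaths bring the pooled milestone forward, and H1 is tested earlier and on fewer deaths than its power statement needs. Because H1 is the gatekeeper, a missed H1 ends the whole sequence.

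There is also a question of conduct. The trial is open label, and two defensible dates for the primary analysis should not both be available.

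**Working it through.** **Inputs.** Protocol 8.1.1: one-sided 2.5%; power 91.7%; target effect "corresponding to a Hazard Ratio (HR) equal to 0.54"; "a median OS of 7 months is expected in the mixed control arm"; accrual of 10 per month for 12 months, then 20 per month to 240 patients at month 18; 13 further months of follow-up (month 31). Protocol summary: 1:1:1 allocation, so 80 per arm. Assumptions added here: exponential survival and no dropout (none is stated). Protocol 8.3 sets the final level at 0.02499; this changes power by less than 0.01 percentage point, so 0.025 is used.

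**Step 1. Reproduce the per-comparison count.** Schoenfeld's formula with equal allocation:

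d = 4 × (1.960 + 1.385)² / (ln 0.54)² = 117.9, so 118.

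Power(d) = Φ(|ln 0.54| × √(d/4) − 1.960). At d = 118: Φ(0.6162 × 5.431 − 1.960) = Φ(1.387) = 91.7%. This matches the plan.

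**Step 2. Reproduce the pooled count.** Expected deaths in an arm at calendar time T are the integral over entry times u of (accrual rate / 3) × [1 − exp(−λ(T − u))], with λ = ln 2 / median. With both HRs at 0.54, the total reaches 170 at month 30.4 (plan: 31). The split is 67.4 control + 51.3 + 51.3, so each comparison has 118.7. The figures 170 and 118 therefore agree under the design assumption.

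**Step 3. Let the arms differ, with 170 as the trigger.**

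| Arm 1 HR | Arm 2 HR | Month of 170th death | Control / Arm 1 / Arm 2 deaths | H1 deaths | H1 power at HR 0.54 |
|---|---|---|---|---|---|
| 0.54 | 0.54 | 30.4 | 67.4 / 51.3 / 51.3 | 118.7 | 91.9% |
| 0.54 | 0.75 | 28.4 | 64.6 / 48.1 / 57.3 | 112.7 | 90.5% |
| 0.54 | 1.0 | 26.95 | 62.2 / 45.5 / 62.2 | 107.8 | 89.2% |
| 0.54 | 1.2 | 26.2 | 60.8 / 44.0 / 65.2 | 104.8 | 88.4% |

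For the third row: Φ(0.6162 × √(107.8/4) − 1.960) = Φ(1.239) = 89.2%.

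Simulation of 20,000 trials with an unstratified log-rank test agrees. With Arm 2 at HR 1.0, H1 has a mean of 107.8 deaths (95% range 102 to 114), is below 118 in 99.9% of trials, and has 88.6% power. When both arms work, simulated power is 91.3%. Uniform accrual over 12, 18 or 24 months gives 107.6 to 108.0 H1 deaths.

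**Step 4. Use 118 in each comparison as the trigger.** With Arm 1 at HR 0.54 and Arm 2 at 1.0, the 118th death in Arms 1 and 3 is expected at month 30.1. That is 30.15 − 26.95 = 3.2 months later than the pooled trigger. About 185 deaths have then occurred in total, and H1 power returns to 91.7% (simulated 91.2%).

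**Step 5. Allow for the futility look.** Protocol 8.3 gives a 60% chance of stopping an arm with progression-free survival HR 1.0. If Arm 2 is stopped, Protocol 8.5 switches to 118 deaths in the one remaining comparison. Weighted H1 power: 0.6 × 91.7 + 0.4 × 89.2 = 90.7%. This is approximate: it takes an arm with no OS effect to have no PFS effect, and it ignores the shared control arm and Arm 1's own futility risk.

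**The case against.** **The SAP already carries the right count.** SAP 4.4 and 6.0 use 118 per comparison, which removes the shortfall if the SAP governs. This largely stands, but nothing says that it governs. SAP 4.6 openly explains where its testing order departs from an earlier protocol; no such statement covers the event trigger, and the SAP's list of major changes does not mention it. SAP 3.0 refers to protocol version 6, while Appendix L of the present protocol refers to version 7 and the text still carries 170.

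**Both rules are minima and can be met together by waiting for the later one.** True, and the bracket in Protocol 8.2.3.1 can be read that way. A reader might infer that the documents contradict each other outright; they do not. The gap is that no sentence requires the joint reading, and Protocol 8.5 alone would allow analysis at 170.

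**Protocol 8.5 and SAP 6.0 define end of study, not a data cut-off.** Also true: each adds a database freeze and a waiting period after treatment. But 8.5 defines when the primary endpoint is mature, and SAP 10.3 gives no cut-off rule.

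**The counts do not agree only at HR 0.54.** A reader might infer that any departure from HR 0.54 in both arms starves H1. That is wrong. H1 has at least 118 deaths whenever Arm 2 contributes 52 or fewer of the 170. At HR 0.50 in both arms each comparison has 119.3; if only monotherapy works, H1 has 124.5 (and H2 107.8).

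**The loss is small and conditional.** It is 2.5 points at worst in the main scenario, and only if an inactive Arm 2 passes a look that stops it 60% of the time. This stands.

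**Conclusion.** The point holds as an unreconciled trigger with a modest power cost. The figures 118, 170 and 91.7% are all correct under the stated assumptions, so this is not an error in the sample-size calculation. The documents do not support a claim that the trial is materially underpowered, and type I error is not at issue.

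What is established: when both comparisons are open, the protocol's maturity rule can be met with fewer than 118 deaths for H1, while the SAP's cannot. If monotherapy is the weaker arm and continues, H1 has about 108 deaths and 89.2% power at monotherapy HR 1.0 (2.5 points below 91.7%), and about 113 deaths and 90.5% at HR 0.75 (1.2 points below). Averaged over the stated futility probability, the HR 1.0 case gives roughly 90.7%.

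These figures rest on a combination HR of 0.54, exponential survival, a 7-month control median, the planned accrual, 80 patients per arm and no dropout. The H1 death count hardly changes across the accrual patterns tried.

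**What to change.** In Protocol 8.1.1, 8.2.3.1, 8.5 and the summary, state that the OS analysis takes place when at least 118 deaths have occurred in each ongoing comparison with control. Put the same sentence in the SAP as an explicit OS data cut-off rule, separate from the end-of-study definition.

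Keep 170 only as the expected total if both HRs are 0.54, and state no upper limit on the total. The 185 in Step 4 is not a ceiling: HRs of 0.54 and 1.2 give about 189.

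**Cost.** One sentence in each place and no extra patients. The cut-off may come about 3 months later than under the 170-death trigger. It falls at about month 30 if the combination HR is 0.54 and monotherapy is no better than that, which is inside the planned 31 months. It comes later if an arm does better than planned: with HR 0.40 in one arm, at about month 33.6.
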